SIBO is by definition a concentration of $\geq 1 \times 10^5$ coliform bacteria cfu per ml from a jejunal aspirate, however there is debate whether 1×10^3 cfu/ml may be more appropriate to define SIBO (9). Jejunal aspirate as a method of diagnosis is however expensive and highly invasive, therefore hydrogen and methane breath testing (HMBT) is most commonly used to diagnose SIBO in the clinical setting. HMBT utilises the gases produced by intestinal microflora to determine whether SIBO or dysbiosis is present in a patient. These microbiota not only produce gases during fermentation of ingested sugars, but other waste products, such as water and short chain fatty acids, which can alter conditions in the small bowel, causing troublesome abdominal symptoms (10).

Silicolgel is a liquid gel containing silicon dioxide as hydrated silicic acid in a colloidal form. The particles of polymeric Silicic acid are highly adsorptive due to large particle surface area and negatively charged surface hydroxyl groups. This allows Silicolgel, when ingested, to encompass large volumes of intestinal gases, inorganic molecules, water and organic molecules such as the waste products of bacterial fermentation. The efficacy of Silicolgel has been demonstrated in an (unpublished) study by [name] -Medstat Research, Lillestrom, Norway. Also an observational study of Silicea gel, a medical device with almost identical formulation to Silicolgel, demonstrated a significant reduction in both upper and lower abdominal symptoms over a 6 week treatment period (11).

This study has been designed to establish whether Silicolgel effects HMBT values and upper and lower GI symptoms, in patient's on long term PPIs, with persistent reflux and abdominal symptoms.

Proposed timeline

6-months to complete recruitment and lab analysis.

Ethical Considerations

The study will be submitted to the Greater Manchester Research Ethics Committee (REC) for approval.

Proposed budget

40 lactulose HMBT tests and analysis (£10,000); Administrative costs for writing and submitting regulatory approvals + calling patients, sending out kits and questionnaires £1000 – **Total costs - £11,000**

Statistical Methods

Sample size calculation: As this is a pilot study to determine proof of concept, a sample size of 20 will be used.

Statistical analysis:

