Primary outcome: Mean change in cumulative total breath hydrogen and methane, from baseline HMBT to end of study HMBT, will be calculated statistically using 2 tailed Paired T-test.

Secondary outcomes:

- Difference between baseline and end of study IBS-SSS scores will be calculated statistically using 2 tailed Paired T-test.
- Difference between baseline and end of study reflux scores will be calculated statistically using 2 tailed Paired T-test.
- Change in bowel habit and abdominal symptoms from baseline to end of study as measured by daily bowel diaries

Study Timelines

Recruitment

Participants will be recruited through gastroenterology clinics at the Functional Gut Clinic as well as through advertisement on several social media platforms. If potential participants register interest, they will be provided with a patient information sheet and consent form to review for at least 24 hours. A screening questionnaire will be carried out to establish whether they are eligible to enter the study. If participants are eligible and have reviewed the study information, they will be enrolled into the study on giving a signature of informed consent.

Day 0

Once participants have enrolled on the study, they will arrange a date to visit the clinic to complete a hydrogen and methane breath test (HMBT), the test will be completed on day 1. The day before the trial, day 0, the participant will be required to follow a specific low residue diet as part of breath testing preparation (appendix 1).

Day 1

On day 1 of the trial, participants will visit The Functional Gut Clinic (FGC) to complete a HMBT following FGC protocol (appendix 2). Participants will also be asked to complete a Reflux questionnaire (appendix 3), IBS-SSS questionnaire (appendix 4) and Bristol stool questionnaire (appendix 5). Following completion of the HMBT and questionnaires, participants will be given a 10 day supply of the blinded product Silicolgel and provided with instructions on how to use the product (appendix 6).

Day 2-11

Participants will be asked to commence ingestion of Silicolgel on study days 2 – 11, as per instructions. Participants will take 15ml of Silicolgel three times daily, 1 hour before meals. On day 11 participants will be required to complete a low residue diet in preparation for HMBT on day 12.

Day 12 (end of study visit)

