9. Participant has had previous abdominal or colorectal surgery except appendectomy, cholecystectomy, or hysterectomy.
10. Participant has previously taken Silicolgel in the past month
11. Participant has a known hypersensitivity to any of the ingredients of Silicolgel
12. Participant suffers regularly from constipation

13. Participant is involved in any other research projects either currently or during the previous month

Test Product, Planned Doses, Mode of Administration and duration of treatment

Silicolgel 15ml, oral administration. Total Participation is expected to last 12 days, with a 10-day treatment period. During the treatment period participants will take 15ml Silicolgel three times daily. Silicolgel should be taken one hour before meals. Silicolgel may be taken undiluted or diluted with water. Due to its inability to be absorbed into the blood stream and physical not pharmacological mechanism, Silicolgel is considered a class IIa medical device according to the Medical Device Directive 93/42/EEC Annex rule 5.

The bottle must be shaken before each administration. The bottle of Silicolgel should be stored above 2°C. After opening the bottle, the product should be consumed within 3 months, and it should not be used after the date given on the label.

Blinding procedure

All participants will be blinded to the study device. Silicolgel bottles will be labelled without any Silicolgel branding or product ingredients. Study participants will be made aware that the product is a CE marked medical device that works via intestinal adsorption. Any potential side effects of the product will also be disclosed to the patient.

Study Outcome Assessments

Primary outcome assessment

Mean change in cumulative total breath hydrogen and methane, will be determined from baseline HMBT to end of study HMBT. Cumulative total hydrogen and cumulative total methane will be calculated independently of one each other. Breath hydrogen and breath methane will be measured in units of parts per million (ppm). Statistical significance will be determined using a paired t-test ($p < 0.05$).

Each HMBT samples will be analysed using gas chromatography analysis on the day of the breath test being carried out. Breath carbon dioxide will also be measured in order to verify the validity of each sample and apply a correction factor. A correction factor above 2.5 ($CO_2 < 2\%$) is considered an invalid sample.

Secondary outcome assessment

Reflux Questionnaire (Appendix 3)

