- 7) Copy of the REC approval of recruitment advertising (if applicable);
- 8) A list of REC members and their qualifications, and a description of the committee's working procedures.

During the study, the Investigator must maintain the following essential/administrative documents related to the study:

- 1) Copy of the signed Protocol Signature Page
- 2) Copy of financial disclosure form(s) for the Investigator and all sub-Investigators
- 3) Curricula vitae of any new Investigator(s) and/or sub-Investigators involved in the study
- 4) Adverse Event Reports
- 5) Updates of laboratory/technical procedures/tests
 - a. Normal value(s)/range(s)
 - b. Certification
 - c. Accreditation
 - d. Established quality control and/or external quality assessment
 - e. Other validation (where required)
- 6) Responsibility Log
- 7) Other logs (screening, enrolment, etc.)
- 8) Signed ICFs
- 9) Validated questionnaires
- 10) CRFs

Case Report Forms and data management

All data relating to the study will be recorded in the participant's CRF. The CRFs are to be completed at the time of the participant's visit, except for results of tests performed outside the Investigator's office. CRF data should indicate the participant's participation in the study and should document the dates and details of study procedures, AEs, all observations, and participant status. The Investigator is responsible for verifying that all data entries on the CRFs are accurate and correct and ensure that all data are entered in a timely manner, as soon as possible after information is collected. An explanation should be provided for all missing data. The Investigator must provide his or her formal approval of all the information on the CRFs and changes to the CRFs to endorse the final submitted data for the participants for which he or she is responsible.

The CRFs will be in the form of paper and will be stored initially in locked filing cabinets in the Functional Gut Clinic and subsequently archived.

A record of participant screen failures will be maintained for participants who do not qualify for enrolment, including the reason for the failure

Reference List

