- Confirm the patient has stopped required medication, followed the pre-study diet and fasted for the past 12 hours.
- Explain the test procedure, benefits and risk of the test and obtain written consent using the consent form.

Procedure Method

- Collect a baseline breath sample by asking the patient to insert the straw halfway into the tube and breath through the straw until they see condensation. They can then remove the straw and replace the cap.
- Ensure to fill out all the information on the collection tube label and adhere to each tube after sample collection.
- Ask the patient if they are experiencing any symptoms (specifically bloating, nausea or abdominal pain) at the beginning of the test. Ask them to rate each symptom on a scale of 0 – 10 (with 0 being no symptoms and 10 being severe symptoms) and record the results on the symptom score sheet.
- Mix the substrate sachet with 200ml drinking water and instruct the patient to drink it.
- Continue to take samples and note symptoms every 15 minutes until 10 samples have been collected (full test duration is 2 hours and 15 minutes). Invite the patient to sit in the waiting room for the rest of their test.
- When collecting the 10th sample, invite the patient back into the clinic room and explain that results will be sent out electronically to the referring doctor in 48 hours.
- Ask if they have any questions

After the procedure

- Ensure all 10 collection tubes are labelled correctly and pack them into the bubble wrap pouches. Put the pouches and the symptom sheet back into the kit box and post back to Functional Gut Diagnostics.
- Dispose of the plastic cup and straw.

Reporting the results

- Once the Functional Gut Diagnostics technical report is uploaded to DGL, an TFGC cover letter will be written using the report template. This will be saved and sent as a PDF file.
- Templates are available on each TFGC laptop/ computer on the desktop and have been emailed to each member of staff at TFGC.

Clinic risk assessment

- A clinical risk assessment has been made regarding this procedure which is available as a hard copy in the Clinic Registry folder and has been emailed to each member of staff at TFGC.

How the results will be communicated?

- If the patient consents, during the consent process, to allowing TFGC to email reports to the referring consultant then this will be the only option.

- If the referrer or patient requests another method then the use of fax will be used.

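### Does the primary cumulative total need a written formula and a rule for invalid breath samples before the data are seen?

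*Combined protocol and SAP*

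**What the plan says.** The Primary outcome assessment sets the endpoint as "Mean change in cumulative total breath hydrogen and methane, will be determined from baseline HMBT to end of study HMBT". Statistical Methods uses nearly the same words, "Mean change in cumulative total breath hydrogen and methane, from baseline HMBT to end of study HMBT", and names a two-tailed paired t-test. The gases are kept apart: "Cumulative total hydrogen and cumulative total methane will be calculated independently of one each other". Readings are in ppm. On sample quality the plan says "Breath carbon dioxide will also be measured in order to verify the validity of each sample and apply a correction factor", and a sample with a factor above 2.5 (CO2 under 2%) "is considered an invalid sample".

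Appendix 2 (Procedure Method) fixes the sampling: every 15 minutes "until 10 samples have been collected (full test duration is 2 hours and 15 minutes". Under Statistical Methods, "a sample size of 20 will be used", on the ground that this is a proof-of-concept pilot. The only text on missing data, under Case Report Forms and data management, concerns record keeping: "An explanation should be provided for all missing data".

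The text reviewed does not say whether the total is a sum or an area under the curve, whether the pre-substrate sample counts, or what an invalid sample does to the total.

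**The concern.** The plan creates a category of invalid samples and leaves its consequence for the primary endpoint blank. If the total is a plain sum over whatever samples survive, each lost non-zero sample pulls that visit's total down. Equal loss at both visits adds noise to 20 paired differences. Heavier loss at the second visit would look like a fall in gas, and heavier loss at the first could hide one. There is no control arm to cancel such an imbalance. A rule settled at analysis would be chosen with the values and the visit labels in view. At stake would be a spurious or masked change in the primary outcome, carried into the design of the larger randomised trial that the Methodology section mentions.

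**Working it through.** **1. The plan's own figures.** Ten samples 15 minutes apart span (10 - 1) x 15 = 135 min, which is the stated 2 h 15 min. Two tests for each of 20 people make 40, as budgeted, and 40 x 10 = 400 samples. The sample size of 20 has no effect size, SD or power behind it, so there is no calculation to reproduce.

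**2. Sum or area.** With ten equally spaced samples the trapezoid area is 15 x [sum - (first + last)/2]. A flat 20 ppm profile gives a sum of 200 ppm and an area of 15 x (200 - 20) = 2700 ppm.min. The two differ in unit and in half-weighting the end samples. An area would carry ppm x time. The plan's word is total and its only unit is ppm, which points to the sum, although ppm is stated for the breath reading and not for the total.

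**3. One lost sample.** The profiles are assumed, because the documents give none.

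| Profile (ppm) | Sum | Change in unadjusted sum |
|---|---|---|
| Flat 20 | 200 | -20/200 = -10% |
| Rising 8, 8, 9, 10, 12, 16, 22, 30, 38, 45 | 198 | -8/198 = -4% to -45/198 = -23% |
| Steep 4, 4, 4, 5, 6, 10, 20, 40, 60, 50 | 203 | -4/203 = -2% to -60/203 = -30% |

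**4. How often a rule is needed.** With independent losses at rate q, the chance that a participant's 20 samples include at least one invalid is 1 - (1 - q)^20. This is 18% at q = 1%, 33% at 2%, 64% at 5% and 88% at 10%. The analyst will therefore probably have to do something.

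**5. What the unadjusted sum costs.** Simulation: n = 20, paired t-test on ppm, 20,000 trials per setting, the three profiles above. Assumed log-SDs: between-person 0.8, between-visit 0.3 or 0.15, per-sample 0.2. Power is for an assumed true change of -25%; without loss it is 55-58% (log-SD 0.3) or 94-96% (0.15).

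- Equal loss, power points lost: 0.3-1.5 at 1%, 0.9-2.4 at 2%, 2.5-6.9 at 5%, 4.7-14.9 at 10%. Null rejection stays at 3.5-4.0%.
- Unequal loss, no true change, 1% then 2%: shift 0.98/0.99 - 1 = -1%. Null rejection is 3.5-4.1%, against 3.4-4.0% with no loss.
- Unequal loss, 5% then 10%: shift 0.90/0.95 - 1 = about -5%. Null rejection is 5.5-5.7% (log-SD 0.3) or 8.0-9.2% (0.15).
- Unequal loss, 0% then 10%: shift -10%. Null rejection is 10-11% or 22-28%.

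The large figures need a loss rate of 5-10%, and the error inflation also needs the loss to be unequal between visits. The documents support neither.

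**6. What a sensible analyst would do.** Using the mean of the valid samples removes the dependence on how many survived. With complete data it is the sum divided by 10, so the t-test is identical. In simulation it holds null rejection at 3.4-4.2%. At 10% loss in both visits its power is 50-56% or 85-96%, against 47-52% or 79-90% for the unadjusted sum.

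**7. Is one rule clearly best?** Using only time points valid at both visits gives 54-56% or 92-95% power at 10% independent loss. But it discards valid samples and lets time points differ between people. If losses cluster strongly within participants and at least 5 of 10 paired points are required, it excludes about 2 of 20. Its power at log-SD 0.3 is then 49-52%, against 47-53% for the plain sum, so the gain may vanish. At 1-2% loss the mean of valid samples is within about 1.5 power points of it. An area that bridges gaps copes well with most interior losses, but loses 11%, 24% or 31% on the three profiles if the last sample goes.

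**The case for a change.** The strongest case for a change is that the omission concerns the primary endpoint and the remedy is a few sentences. Even at 1% invalid, about 20 x 0.18 = 3.6 participants would have an incomplete pair. Nothing provides for re-collecting a bad sample. The clinic's check at collection is visible condensation, whereas validity depends on CO2 measured later. With one arm and no described blinding of the analyst to visit, a rule chosen late could be chosen to suit the result.

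Much of this stands as description. The formula and the rule are unwritten, a choice will probably be needed, and writing it down would cost almost nothing. It does not show that the plan as written leads to a wrong result. The damaging scenarios assume an analyst who knows a sample is invalid and still adds up nine values against ten. They also assume loss rates that the documents do not give. CO2 is measured on every sample, so a count of invalid samples by visit would expose any imbalance. Power lost against an assumed -25% effect is also a yardstick that the plan never adopts: it is an exploratory pilot with no power target.

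**Conclusion.** The observation is accurate but calls for no change. The gap is missing detail of a kind that analysts fill in the ordinary course: a sum of CO2-corrected ppm values per gas, put on a common footing when a sample is invalid. At 1-2% loss the cost is at most 2.4 power points even with the crudest handling, and no error inflation is visible. With ordinary handling, null rejection stays near 3-4% throughout. The choice among averaging valid samples, pairing time points and interpolating is a trade-off with no clear winner. Whether the pre-substrate sample counts belongs to the same gap; a total over the ten samples includes it.

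This rests on assumed invalid rates, gas profiles and variances, on a treatment effect proportional at all time points, and on losses that are mostly independent. The view would differ if invalid samples ran at 5% or more, fell unevenly between visits, and the result were reported as an unadjusted sum. Part of the patient breath-test leaflet and the laboratory's own reporting procedure were not available. The leaflet is an unlikely place for an analysis rule.

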The Functional Gut Clinic
[name]
London
[name]
Phone: [name]
Fax: [name]
[contact]
Email: [contact]

Principle Investigator – [name] Ph.D. - Consultant Clinical Scientist

Pilot Study – The effect of an intestinal adsorbent on hydrogen and methane breath testing, in patients with abdominal and reflux symptoms, on long term proton pump inhibitor therapy

Title of Study

The effect of an intestinal adsorbent on hydrogen and methane breath testing, in patients with abdominal and reflux symptoms, on long term PPI therapy

Study Sites

The Functional Gut Clinic Manchester – [name]

Objective

[figure not shown]
To determine the effect of Silicolgel on hydrogen and methane breath testing in patients on long term PPI therapy with reflux and abdominal symptoms.

Methodology

This protocol describes a pilot study, using an uncontrolled, open label single-armed design, consisting of two distinct periods (pre-treatment and treatment). Participants visiting a gastroenterologist at The Functional Gut Clinic or recruited through advertising on social media platforms should be eligible for the study as long as they have no concomitant exclusionary disease and meet inclusion criteria for the study.

This pilot study will be used to explore the question outlined in the objective and to determine the feasibility of carrying out a larger randomised controlled trial

Study timeline

Background

Proton pump inhibitors (PPIs) are the most commonly prescribed drugs worldwide and have shown impressive efficacy in the reduction of oesophageal mucosal damage associated with GORD and symptoms relating to GORD (1, 2). There is, however, growing evidence to show a large percentage of patients receiving long term PPI therapy, develop IBS type symptoms such as abdominal discomfort, pain, bloating, belching and altered bowel habit (3, 4). It has been proposed that the development of these symptoms may be linked to shifts in the location, concentration and species of gastrointestinal micro flora. Inhibition of gastric acid secretion, through PPI therapy, has been linked to small intestinal bacterial overgrowth in several studies (5-7). A meta-analysis interrogating the relationship between PPI use and SIBO, confirmed there was a significant relationship between PPI therapy and SIBO (8).

[figure not shown]

Figure 1 : Symptom pattern change in long term PPI users (*P<0.05, **p<0.01, *p<0.001) (4).**

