Participants will visit The Functional Gut Clinic (FGC) to carry out a repeat HMBT following FGC protocol (appendix 2). Participants will also be asked to repeat the Reflux questionnaire (appendix 3), IBS-SSS questionnaire (appendix 4) and bowel habit questionnaire (appendix 5). Completion of the repeat breath test and questionnaires will mark the end of the study for the patient.

Eligibility

Inclusion Criteria

1. Participant has provided written informed consent before participating in the study after being given a full description of the study and prior to any study-specific procedures being performed.
2. Patient has been taking PPI therapy for >6 months
3. Patient reports bloating ≥ 3 on screening questionnaire
4. Patient reports one of the following ≥ 3 on screening questionnaire - belching, heartburn, nausea, reflux sensation
5. Participant is a male or non-pregnant female and is age 18 years of age or above
6. Participant is able to communicate well with the Investigator and to comply with the requirements for the entire study.
7. Patient has capacity to understand written English
8. Patient agrees to follow pre-test diet for 24 hours before giving test sample (Appendix A).
9. Participant agrees to refrain from strenuous physical activity on the day of the breath test.
10. Participant agrees to refrain from smoking on the day of the breath test
11. Participant agrees to an overnight fast on the night before the breath test. Food and drink must be withheld until after all breath test samples have been taken.
12. Participant agrees to not take any probiotic for 7 days before the breath test.
13. Participant has a body mass index (BMI) between 18.5 and 34.9kg/m² (bounds included).

Exclusion criteria

1. Participant reports using any prohibited medication, medical device or supplementation
2. Participant has taken antibiotics or undergone colonoscopy/sigmoidoscopy in the 4 weeks prior to enrolment.
3. Participant has a diagnosis of any organic gastrointestinal disease, including inflammatory bowel disease, coeliac disease and diverticulitis.
4. Participant has known mechanical obstruction of the GI tract
5. Participant has diabetes
6. Participant has any hepatic disease
7. Participant has any disease of the CNS
8. Participant is involved in this study as an Investigator, sub-Investigator, study coordinator, other study staff, or Sponsor member.

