SADEs, SAEs, and USADEs should always be recorded in the CRF and reported to the Sponsor using the Sponsor's SAE reporting form. Any SAEs that occur during the screening period that resulted from the administration of any study procedures and are unexpected, should also be reported. The form should be emailed to [contact] ([name]) within 24 hours of the site team becoming aware of the event, and the Principle Investigator should be copied in this email ([contact]). If the site does not receive an acknowledgement of the receipt of the report within 24 hours, they should immediately contact the Principle investigator.

The Sponsor should also report all serious adverse events, whether initially considered to be device related or not, immediately to the MHRA

Concomitant medication, medical device or supplementation

Restrictions regarding concomitant medicines are described below. All concomitant medicines taken from the time of informed consent at the Screening Visit through the End of Treatment Visit will be recorded on the appropriate concomitant medicine page of the participant's CRF.

28 days prior to Visit 1

- 1) Participants must have not taken any oral or parenteral antibiotic medication at least 28 days prior to visit 1. Participants must not commence any antibiotic therapy from signature of informed consent until after the end of study visit or have withdrawn participation
- 2) Participants must not have used Silicolgel at least 28 days prior to visit 1.

7 days prior to visit 1

- 1) Participants must not have used laxative therapy at least 7 days prior to visit 1 and not use any laxative therapy for the duration of the study.
- 2) Participants must not have taken a probiotic product at least 7 days prior to visit 1 and must refrain from using any probiotics until after the end of study visit or have withdrawn participation.

From Day 0 to end study

All medicines, medical devices and supplementation listed in this section are excluded from day 0 for the duration of the study.

- 1) Any investigational drugs.
- 2) All narcotics either alone or in combination (e.g., tramadol, codeine, morphine, propoxyphene, loperamide, diphenoxylate, and paregoric).
- 3) Any medicine that is known to cause diarrhoea
- 4) Any over-the-counter or prescription laxative, suppository, or enema.
- 5) Any anti-spasmodic medication
- 6) Any other medical advice with adsorptive properties
- 7) Any medical device affecting gastrointestinal motility

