- 8) Antidepressants unless the participant has been on a stable dose for at least 1 month before visit 1 and there is no plan to change dose during the investigation.

Study Operations

Good Clinical Practice

This study will be conducted according to the protocol and in compliance with ICH GCP, the ethical principles stated in the Declaration of Helsinki, and other applicable regulatory requirements.

The Investigator confirms the above by signing the protocol.

Termination of Participants

Participants will be informed that they have the right to withdraw from the study at any time for any reason, without prejudice to their medical care. The Investigator will make reasonable efforts to keep each participant in the study. However, if the Investigator removes a participant from the study or if the participant declines further participation, the evaluations required at the end of study visit should be performed if possible. All evaluations and observations, together with the description of the reason(s) for study withdrawal, must be recorded on the appropriate page of the participant's CRF.

The following are justifiable reasons for the Investigator to withdraw a participant from the study:

- The occurrence of an AE;
- Withdrawal of consent;
- Unforeseen events: any event that, based on the Investigator's judgement, makes further treatment inadvisable;
- Serious violation of the study (including persistent participant attendance failure and non-compliance).

An effort must be made to determine why a participant fails to return for the necessary visits or is dropped from the study. Regardless of the reason for termination, all data available for the participant at the time of discontinuation of follow-up should be recorded where applicable on the CRF. All reasons for discontinuation of treatment should be documented.

Financial Disclosure

Relevant financial disclosures will be included in the submission to the ethical committee.

Essential Documents

- 1) Current, signed curricula vitae of the Investigator and all sub-Investigators;
- 2) Copy of current medical license of the Investigator and all sub-Investigators (as applicable);
- 3) Copy of Research Ethics Committee (REC) approved Participant information sheet;
- 4) Evidence of Sponsor insurance or indemnity;
- 5) Copy of the REC approval letter for the protocol and informed consent;
- 6) Copy of the REC-approved informed consent document to be used;

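### Prohibited-list item 6 cannot be applied as printed and, read as 'device', does not bar adsorbent medicines or supplements

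*Combined protocol and SAP*

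**What the plan says.** The rule is in the protocol section on concomitant medication, medical device or supplementation, under the list that runs from Day 0 to the end of the study. The lead-in limits the bar to what is listed: "All medicines, medical devices and supplementation listed in this section are excluded from day 0 for the duration of the study". Item 6 reads "Any other medical advice with adsorptive properties" and item 7 reads "Any medical device affecting gastrointestinal motility".

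The other items on that list bar:
- investigational drugs (item 1);
- narcotics, with loperamide and diphenoxylate among the examples (item 2);
- medicines known to cause diarrhoea (item 3);
- laxatives, suppositories and enemas (item 4);
- antispasmodics (item 5);
- antidepressants, "unless the participant has been on a stable dose for at least 1 month before visit 1" and no dose change is planned (item 8).

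Earlier parts of the section set washouts before visit 1. These are 28 days for antibiotics and for Silicolgel, and 7 days for laxatives and probiotics. For probiotics the bar carries on through the study: participants "must refrain from using any probiotics until after the end of study visit".

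Exclusion criterion 1 reads "Participant reports using any prohibited medication, medical device or supplementation" and names no product of its own.

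**The concern.** Item 6 protects the question that the study asks. The Background describes Silicolgel as a highly adsorptive gel that takes up intestinal gas and the waste products of fermentation, and the Blinding procedure section says participants will be told that it works by intestinal adsorption. A second adsorbent would act through the same claimed mechanism on the same outcomes: cumulative breath hydrogen and methane, and abdominal symptoms.

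The Methodology section describes the study as "using an uncontrolled, open label single-armed design", and the primary analysis is a paired t-test of the change from baseline. A participant who starts another adsorbent between the two breath tests contributes that product's effect to the change, most likely in the direction that favours Silicolgel. A control arm would show how much change occurs without Silicolgel; this design has none. Participants must score at least 3 for bloating and for one upper-gut symptom to enter, so self-treatment is plausible, although the documents do not say how common it is.

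**Working it through.** The defect is in the wording, so the main check is to read the rules side by side. The plan states no figure to reproduce.

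**1. Item 6 as printed.** Advice has no adsorptive properties, so the item excludes no product.

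**2. Item 6 repaired.** The closest repair is 'device' for 'advice', which matches the wording of item 7. An adsorbent sold as a medicine or a food supplement then falls outside the item, although the section title and lead-in cover all three product types.

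**3. Whether another rule closes the gap.** Items 1 to 5 and 8 do not name adsorbents. The 28-day rule covers Silicolgel only. The 7-day rules cover laxatives and probiotics. Exclusion criterion 1 depends on the list and adds nothing to it. So no rule in the available text bars an adsorbent medicine or supplement as such.

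**4. Which use matters.** Unchanged use before and throughout would be present at both tests and adds no new shift between them. A product started between Day 1 and Day 12 does. So could a product stopped at Day 0, one day before the baseline test, because its effect might still be present at baseline and gone by Day 12. A repair of item 6 therefore needs a washout as well as better wording.

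**5. Rough size.** The sample size is from the Statistical Methods section: "a sample size of 20 will be used". The documents give neither a usage rate nor an effect size, so the next two inputs are assumptions: k participants who newly start an adsorbent (1 or 2), and d, the favourable shift in their own change, in SDs of the paired change (0.5 to 1.0).

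- Shift in the mean change = k × d / 20.
- Low end: 1 × 0.5 / 20 = 0.025 SD.
- High end: 2 × 1.0 / 20 = 0.10 SD.
- For scale, the half-width of the 95% confidence interval for the mean change with all 20 analysed is t(0.975, 19 df)/√20 = 2.093/4.472 = 0.468 SD.
- Ratios: 0.025/0.468 = 5% and 0.10/0.468 = 21%.

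Under these assumptions the shift is well inside the study's own imprecision.

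**The case against.** The best reply is that item 6 is a typing slip with an obvious intent. It says 'any other', the section title covers medicines, devices and supplements, and site staff would probably apply it that way. The intent is indeed clear, but the rule decides who may enrol and what may be taken, and its most natural correction gives a narrower rule than the intent.

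A second reply is that use would be seen. The section requires all concomitant medicines from consent to the End of Treatment Visit to be recorded in the CRF. This has force. A reader might infer that the effect of another adsorbent could never be told apart from that of Silicolgel. The documents do not support that, because with 20 participants a recorded new medicine could be identified and those participants described or set aside in a sensitivity analysis. Two limits remain: the recording sentence names medicines only, so capture of supplements is less certain, and the plan gives no analysis rule for such use.

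A third reply is that the breath-test instructions may cover the gap. On the test morning the leaflet tells patients to avoid anything that could affect the bowel and refers to a preceding list, and Appendix 2 has staff confirm that required medication was stopped. That list is not in the text available here, so it cannot be called absent, and it may limit use around both tests. The visible instruction concerns test preparation; whether the list reaches the treatment days cannot be checked.

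A reader might also infer from item 7 that motility medicines are left open. The documents do not support that as a material gap. Items 2 to 5 already bar most of them, regular constipation is an exclusion, and the unavailable list may cover the rest around the tests. For whatever remains, such as a prokinetic not known to cause diarrhoea, the direction of any effect is unknown.

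**Conclusion.** The point holds for item 6, as a low-cost improvement. As printed the item bars nothing, and read as 'device' it leaves adsorbent medicines and supplements permitted in an uncontrolled before-after test of an adsorbent. The likely effect is small: a shift of 0.025 to 0.10 SD in the mean change under assumed inputs that the documents neither support nor contradict. The wording defect does not depend on those inputs.

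Nothing here supports a claim that the primary test's error rate is materially wrong or that the pilot's result would be unusable. Two things remain unknown: how many participants use adsorbents, and what the breath-test medication list contains. If that list already bars adsorbents around both tests, the exposure is smaller still for breath gas and remains mainly for symptoms during the treatment days.

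**What to change.** Reword item 6 to: *Any other medicine, medical device or supplement with adsorptive properties.* Bar these products from 7 days before visit 1 until after the end of study visit, on the model already used for laxatives and probiotics. The washout keeps anyone from stopping one day before the baseline breath test.

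The 7-day window matches the recall period of the stool questions but is shorter than the 2-week recall of the reflux questionnaire. If the sponsor wants baseline symptom recall to be clear of such products too, the 28-day rule already set for Silicolgel would cover the 2 weeks, at the price of more exclusions.

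The cost is one reworded item and one added washout line. The downside is possibly a few extra exclusions among users of an adsorbent medicine or supplement. No sample size or analysis changes.

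Optionally, extend item 7 to newly started motility medicines with the stable-dose allowance of item 8. This is tidying only.
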